[figure not shown]

## SYNOPSIS

Title	A Phase 2 Randomized Open Label Crossover Study to Compare ORMD-0801 Given Once Daily at Bedtime to ORMD-0801 given Three Times Daily (45-90 minutes before Meals) in Subjects with Type 1 Diabetes
Indication	Type 1 Diabetes
Clinical Phase	Phase 2
Investigational Medicinal Product (IMP)	Name of the IMP: ORMD-0801 Dose and dosage regimen: Treatment A: 24 mg (16 mg capsule + 8 mg capsule) Once Daily (QD) at bedtime Treatment B: 8 mg (8 mg capsule) three times a day (TID) 45-90 minutes before meals Placebo capsules will be administered to subjects for 10 day run-in period prior to Randomization (subjects will take one capsule daily at bedtime). Formulation: Coated soft gel capsule [SBTI], disodium EDTA, fish oil, aerosol, and Tween 80 Mode of administration: Oral
Primary Objectives	

1. To compare the impact of Oral Insulin dosed QD to Oral Insulin dosed TID on exogenous basal and bolus insulin requirements in subjects with Type 1 Diabetes (T1D) on their regular diet over a 4-week period.

2. To compare the impact of Oral Insulin dosed QD to Oral Insulin dosed TID and associated adjustments of basal and bolus insulin on mean 24-hour glucose and parameters of glycemic variability as measured by a Continuous Glucose Monitor over a 10-day period in subjects with T1D

Secondary Objectives	

1. To compare the change from baseline in number of hypoglycemic episodes in subjects treated with Oral Insulin dosed QD to Oral insulin Dosed TID in subjects with T1D

2. To compare the change from baseline in Plasma A1C levels in subjects with T1D treated with Oral Insulin dosed QD or Oral Insulin dosed TID.

3. To explore changes in glucodynamics between the different dosing regimens.

4. To evaluate the safety of Oral Insulin

Total Sample Size	Approximately 26 completers
Sites	3 sites
Study Design	
This study is a Phase 2 randomized, crossover study comparing ORMD-0801 given QD versus TID in subjects with T1D. Subjects with T1D will have a screening visit (Visit 1) during which they will be required to review and sign the informed consent form. Medical history and demographics will be collected. Vital signs will be measured, physical exam will be performed, and blood and urine samples will be collected for hematology/chemistry/urinalysis.
 
Eligible subjects will be scheduled to return to the clinic in 1 week (Visit 2). Subjects fulfilling all inclusion/exclusion criteria will have a CGM placed, provided with a diary, dispensed Placebo capsules and asked to return to the clinic in 10 Days (Visit 3, Day 1) for randomization. At Visit 3, data from CGM will be downloaded and diaries will be collected. Blood samples will be collected in fasting for chemistry and HbA1c. Subjects will be randomized to receive either ORMD-0801 24 mg given once daily at bedtime, or ORMD-0801 8 mg given three times a day, 45-90 minutes before meals. Subjects will be instructed to continue their normal diet, and to adjust their basal and bolus insulin in the normal fashion. Subjects will be instructed to return to the clinic 10 days before Visit 5 (Visit 4, Day 18). At Visit 4, compliance will be assessed, IMP and diary dispensed and the CGM will be placed. Subjects will be instructed to return to the clinic in 10 days for Visit 5 (Day 28). At Visit 5 a fasting blood sample for chemistry panel and HbA1C will be drawn and after the diary has been collected and the CGM monitor removed, they will be crossed over to the alternate treatment regimen. IMP will be dispensed, and the subject will be asked to return 10 days before Visit 7 for Visit 6 (Day 46). At Visit 6, compliance will be checked, IMP and diary will be dispensed and

	
the CGM will be placed. Subjects will be instructed to return in 10 days for Visit 7 (Day 56). At Visit 7 the CGM will be removed, compliance checked, the diary will be collected, and a blood sample will be drawn for a chemistry panel and HbA1C. A physical examination will be performed, and the subject will exit the study.
 
Subjects will be provided with diaries at Visits 2, 4 and 6, and will be asked to capture the amount of basal and bolus exogenous insulin administered each day and calculate their carbohydrate count for all meals and snacks over the 10-day CGM monitoring period. Diaries will be collected at Visits 3, 5 and 7.

Study Endpoints	
Primary Endpoints:
 

1. To compare the amount of basal, bolus and total (basal + bolus) exogenous insulin utilized over the final 10 days of each treatment period.

2. To compare the impact of Oral Insulin dosed QD to Oral Insulin dosed TID and associated adjustments of basal and bolus insulin on mean 24-hour CGM glucose levels during the final 10 days of each treatment period.

 
Secondary Endpoints:
 

1. Glucodynamics over the final 10 days of each treatment period as measured by CGM:

a. Time in range 70 - 180 mg/dL

b. Time < 70 mg/dL

c. Time >180 mg/dL

d. Time >250 mg/dL

e. Glucose Coefficient of Variation

f. Low Blood Glucose Index (LBGI)

g. Glucose below 70 mg/dL Area Over the Curve (AOC70)

2. Total daily non-oral insulin requirements in units per kilogram (kg) body weight over the last 10 days of each treatment period.

 
Exploratory Endpoints:
 

3. HbA1c measured at the end of each treatment period

4. Patient diary-reported carbohydrate intake over the final 10 days of each treatment period

5. Changes in body weight from baseline (Visit 2) to the end of each treatment period

	
6. Other measures of hypoglycemia over the last 10 days of each treatment period:
 

a. Severe hypoglycemia (SH) events (impaired or loss of consciousness requiring assistance of another)

b. Documented symptomatic hypoglycemia (an event during which typical symptoms of hypoglycemia are accompanied by a measured plasma glucose concentration <70 mg/dl (3.9 mmol/L))

c. Total time <70 mg/dL by CGM

d. Nocturnal hypoglycemia, severe or documented symptomatic episodes (as defined above) occurring after the subject has retired for the primary sleeping period

 
Safety assessments evaluating:
 

• Changes in clinical laboratory tests (hematology, chemistry, urinalysis);

• Collection of adverse events (AEs);

• Changes in Vital sign measurements

Duration of Participation	Including screening period, subjects will participate in this study for about 77 days (11 weeks).
Subject Selection Criteria	
Inclusion Criteria
 
Each subject must meet all of the following criteria to be eligible for study participation:
 

1. Male and female subjects aged 18 and older.

2. Body mass index (BMI) of 19-30 kg/m^2 at Screening and stable weight, with no more than 5 kg gain or loss in the 3 months prior to Screening.

3. T1D subjects must have:

a. A documented history of type 1 diabetes for at least 6 months

b. Should be on an MDI regimen

c. C peptide levels of < 0.7 ng/mL

d. HbA1C ≥ 6.5% to ≤10%

4. Females of childbearing potential must have a negative serum pregnancy test result at Screening.

5. Females who are not of childbearing potential are defined as:

a. post-menopausal (defined as at least 12 months with no menses in women ≥45 years of age) or

	
b. has had a hysterectomy and/or bilateral oophorectomy, or had bilateral tubal ligation or occlusion at least 6 weeks prior to Screening
 
6. Subjects who are of childbearing potential must:
 
a. agree to remain abstinent from heterosexual activity† or agree to use (or have their partner use) acceptable contraception to prevent pregnancy within the projected duration of the trial and for 14 days after the last dose of blinded investigational product. Two methods of contraception will be used to avoid pregnancy. Acceptable combinations of methods include:
 

i. Use of one of the following double-barrier methods: diaphragm with spermicide and a condom; cervical cap and a condom; or a contraceptive sponge and condom

ii. Use of hormonal contraception (any registered and marketed contraceptive agent that contains an estrogen and/or a progestational agent [including oral, subcutaneous, intrauterine and intramuscular agents, and cutaneous patch]) with one of the following: diaphragm with spermicide; cervical cap; contraceptive sponge; condom; vasectomy; or IUD.

iii. Use of an IUD with one of the following: condom; diaphragm with spermicide; contraceptive sponge; vasectomy; or hormonal contraception (see above).

iv. Vasectomy with one of the following: diaphragm with spermicide; cervical cap; contraceptive sponge; condom; IUD; or hormonal contraception (see above).

 
†Abstinence can be used as the sole method of contraception if it is in line with the subject's preferred and usual lifestyle and if considered acceptable by local regulatory agencies and ethics committees. Periodic abstinence (e.g., calendar, ovulation, sympto-thermal, post-ovulation methods, etc.) and withdrawal are not acceptable methods of contraception.

	
Exclusion Criteria

	
Subjects who meet any of the following criteria must be excluded from the study:
 

1. Clinical diagnosis of type 2 diabetes;

2. Evidence of unawareness of hypoglycemia unawareness, a documented plasma glucose <math>\leq 50</math> mg/dL in the absence of symptoms of hypoglycemia at Screening.

3. FPG <math>>300</math> mg/dL at Screening; a single repeat test is allowable.

4. Use of the following medications:

a. Administration of thyroid preparations or thyroxine (except in subjects on stable replacement therapy) within 6 weeks prior to Screening.

b. Administration of systemic long-acting corticosteroids within two months or prolonged use (more than one week) of other systemic corticosteroids or inhaled corticosteroids (if daily dosage is <math>> 1,000</math> <math>\mu</math>g equivalent beclomethasone) within 30 days prior to Screening. Intra-articular and/or topical corticosteroids are not considered systemic.

5. Laboratory abnormalities at Screening including:

a. Abnormal serum thyrotropin (TSH) levels below the lower limit of normal or <math>>1.5</math>X the upper limit of normal

b. Elevated liver enzymes (alanine transaminase (ALT), alanine aminotransferase (AST), alkaline phosphatase) <math>>2</math>X the upper limit of normal.

c. Very high triglyceride levels (<math>>600</math> mg/dL); a single repeat test is allowable.

d. Any relevant abnormality that would interfere with the efficacy or the safety assessments during study treatment administration.

6. Subject has a Screening systolic blood pressure <math>\geq 165</math> mmHg or diastolic blood pressure <math>\geq 100</math> mmHg. Subjects will be allowed to take a BP rescue medication.

7. Any clinically significant ECG abnormality at Screening or cardiovascular disease. Clinically significant cardiovascular disease will include:

a. History of stroke, transient ischemic attack, or myocardial infarction within 6 months prior to Screening,

8. History of or currently have New York Heart Associate Class II-IV heart failure prior to Screening.

9. Presence of any clinically significant endocrine disease according to the Investigator (euthyroid subjects on replacement

--	---

	
therapy will be included if the dosage of thyroxine is stable for at least six weeks prior to Screening).
 
10. Presence of any clinically significant condition (in the opinion of the Investigator) that might interfere with the evaluation of study medication, such as significant renal, hepatic, gastrointestinal (GI), cardiovascular (CV), immune disease, blood dyscrasias or any disorders causing hemolysis or unstable red blood cells, or clinically important hematological disorders (i.e. aplastic anemia, myeloproliferative or myelodysplastic syndromes, thrombocytopenia) at Screening.
 
11. History of gastrointestinal disorders (e.g. hypochlorhydria) with the potential to interfere with drug absorption.
 
12. Presence or history of cancer within the past 5 years of Screening, with the exception of adequately-treated localized basal cell skin cancer or in situ uterine cervical cancer.
 

a. A subject with a history of malignancy >5 years prior to Screening should have no evidence of residual or recurrent disease.

b. A subject with a history of melanoma, leukemia, lymphoma, or renal carcinoma is excluded.

 
13. Positive history of active liver disease (other than non-alcoholic hepatic steatosis), including chronic hepatitis B or C, primary biliary cirrhosis, or active symptomatic gallbladder disease.
 
14. Positive history of HIV.
 
15. Known allergy to soy.
 
16. Subject is on a weight loss program and is not in the maintenance phase, or subject has started weight loss medication (e.g., orlistat or liraglutide), within 8 weeks prior to Screening. Subjects who have had bariatric surgery are also excluded.
 
17. Subject is pregnant or breast-feeding.
 
18. Subject is a user of recreational or illicit drugs or has had a recent history (within 1 year of Screening) of drug or alcohol abuse or dependence. (Note: Alcohol abuse includes heavy alcohol intake as defined by >3 drinks per day or >14 drinks per week, or binge drinking) at Screening.
 
19. At the Principal Investigator's discretion, any condition or other factor that is deemed unsuitable for subject enrollment into the study.

--	--

Statistical Methods	
Subjects will be analyzed under 3 treatment regimens: Standard of Care (Baseline), Once a Day Dosing (QD) and Three Times a Day Dosing (TID).
 
Information collected in the daily diaries or via the Continuous Glucose Monitor (CGM) on the final 10 days of treatment will be analyzed using a Repeated Measures Analysis of Covariance with subject as a random effect with each of the 10 days being a single measure. When analyzing the exogenous insulin variables, CGM parameters (mean 24 hour glucose value and 24 hour time within 70-180 mg/dL range) and patient reported carbohydrate intake will be included as covariates. When analyzing CGM parameters, exogenous insulin (basal and bolus insulin amounts) and patient reported carbohydrate intake will be included as covariates. Treatment least squares means and change from baseline estimates will be derived using this linear model.
 
Information collected at the day 28 visits will be analyzed using an Analysis of Covariance model with subject as a random effect. Treatment least squares means and change from baseline estimates will be derived using this linear model.

----------------------------	---

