## 2 STUDY OBJECTIVES AND ENDPOINTS

### 2.1 Objectives

#### 2.1.1 Primary Objective

1. To compare the impact of Oral Insulin dosed QD to Oral Insulin dosed TID on exogenous basal and bolus insulin requirements in subjects with Type 1 Diabetes (T1D) during the last 10 days of each treatment period.
2. To compare the impact of Oral Insulin dosed QD to Oral Insulin dosed TID and associated adjustments of basal and bolus insulin on mean 24-hour glucose and parameters of glycemic variability as measured by a Continuous Glucose Monitor over the last 10 days of each treatment period.

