#### Secondary Endpoints

3. Glucodynamics over the final 10 days of each treatment period as measured by CGM:
  - a. Time in range 70 - 180 mg/dL
  - b. Time <70 mg/dL
  - c. Time >180 mg/dL
  - d. Time >250 mg/dL
  - e. Glucose Coefficient of Variation
  - f. Low Blood Glucose Index (LBGI)

- g. Glucose below 70 mg/dL Area Over the Curve (AOC70)
4. Total daily non-oral insulin requirements in units per kilogram (kg) body weight over the last 10 days of each treatment period.

Exploratory Endpoints:

5. HbA1c measured at the end of each treatment period
6. Patient dairy-reported carbohydrate intake over the final 10 days of each treatment period
7. Changes in body weight from baseline (Visit 2) to the end of each treatment period
8. Other measures of hypoglycemia:
  - a. Severe hypoglycemia (SH) events (impaired or loss of consciousness requiring assistance of another)
  - b. Documented symptomatic hypoglycemia (an event during which typical symptoms of hypoglycemia are accompanied by a measured plasma glucose concentration <70 mg/dL (3.9 mmol/L))
  - c. Total time <70 mg/dL by CGM
  - d. Nocturnal hypoglycemia, severe or documented symptomatic episodes (as defined above) occurring after the subject has retired for the primary sleeping period

Safety assessments evaluating:

- Changes in clinical laboratory tests (hematology, chemistry, urinalysis);
- Collection of adverse events (AEs);
- Changes in Vital signs measurements

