## 8.4 Continuous Glucose Monitor Evaluation

For the purpose of analysis:

- 24-hour will be considered to be from 6AM to 6AM,
- Daytime will be considered to be from 6AM to 10PM,
- Nighttime will be considered to be from 10PM to 6AM, and

The area under the curve (AUC) will be derived for each of the time periods (24-hour, daytime and nighttime) for each of the 10 days for each treatment regimen. The average glucose measurement will be derived by dividing the AUC by the number of observed hours.

In addition to the mean values, the following CGM parameters will be derived:

- Time in range 70-180 mg/dL
- Time <70 mg/dL
- Time >180 mg/dL
- Time >250 mg/dL
- Glucose coefficient of variation
- Low blood glucose index (LBGI)
- Glucose below 70 mg/dL Area Over the Curve (AOC70)

All of the CGM parameters will be analyzed for each of the time periods (24-hour, daytime and nighttime) using the Repeated Measures Analysis of Covariance Model indicated in Section 8.2.

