2.8. Efficacy Evaluations

The primary endpoints for the study are:

1. To compare the amount of basal, bolus and total (basal + bolus) exogenous insulin utilized over the final 10 days of each treatment period.
2. To compare the impact of Oral Insulin dosed QD to Oral Insulin dosed TID and associated adjustments of basal and bolus insulin on mean 24-hour CGM glucose levels during the final 10 days of each treatment period.

The secondary endpoints for the study are:

1. Glucodynamics over the final 10 days of each treatment period as measured by CGM:
 - a. Time in range 70 – 180 mg/dL
 - b. Time <70 mg/dL
 - c. Time >180 mg/dL
 - d. Time >250 mg/dL
 - e. Glucose Coefficient of Variation
 - f. Low Blood Glucose Index (LBGI)
 - g. Glucose below 70 mg/dL Area Over the Curve (AOC₇₀)
2. Total daily non-oral insulin requirements in units per kilogram (kg) body weight over the last 10 days of each treatment period.

The exploratory endpoints for the study are:

1. HbA1c measured at the end of each treatment period
2. Patient diary-reported carbohydrate intake over the final 10 days of each treatment period
3. Changes in body weight from baseline (Visit 3) to the end of each treatment period
4. Other measures of hypoglycemia
 - a. Severe hypoglycemia events (impaired or loss of consciousness requiring assistance of another)
 - b. Documented symptomatic hypoglycemia (an event during which typical symptoms of hypoglycemia are accompanied by a measured plasma glucose concentration <70 mg/dL)
 - c. Total time <70 mg/dL by CGM
 - d. Nocturnal hypoglycemia, severe or documented symptomatic episodes (as defined above) occurring after the subject has retired for the primary sleeping period.

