2.8.1. Statistical Considerations

Subjects will be analyzed under 3 treatment regimens: Standard of Care (Baseline), Once a Day Dosing (QD) and Three Times a Day Dosing (TID).

Information collected in the daily diaries or via the Continuous Glucose Monitor (CGM) on the final 10 days of treatment will be analyzed using a Repeated Measures Analysis of Covariance with subject as a random effect with each of the 10 days being a single measurement. When analyzing the exogenous insulin variables, the CGM parameters (mean 24 hour glucose value and 24 hour time within 70-180 mg/dL range) and the patient reported carbohydrate intake will be included as covariates. When analyzing CGM parameters, the exogenous insulin (basal and bolus insulin amounts) and patient reported carbohydrate intake will be included as covariates. Treatment least squares means and change from baseline estimates will be derived using this linear model.

Information collected at the day 28 visits (Day 28 and Day 56) will be analyzed using an Analysis of Covariance model with subject as a random effect. Treatment least squares means and change from baseline estimates will be derived using this linear model.

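### As routed through the daily model, glucose CV becomes a within-day measure, nearly insensitive to a QD–TID difference in day-to-day variability, and SAP 2.8.3 does not derive it at all

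*Protocol*

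**What the plan says.** Primary objective 2 (Protocol 2.1.1) covers mean 24-hour glucose and "parameters of glycemic variability as measured by a Continuous Glucose Monitor over the last 10 days of each treatment period". The Protocol's secondary endpoints come under the heading "Glucodynamics over the final 10 days of each treatment period as measured by CGM", and item e is "Glucose Coefficient of Variation". SAP 2.8 repeats it as "e. Glucose Coefficient of Variation". Neither document gives a formula.

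The only model for CGM data is in the Synopsis, Protocol 8.2 and SAP 2.8.1: a "Repeated Measures Analysis of Covariance with subject as a random effect with each of the 10 days being a single measure" (SAP: "with each of the 10 days being a single measurement"). Protocol 8.4 derives AUC and mean glucose day by day, then lists the further parameters, CV among them. It continues: "All of the CGM parameters will be analyzed for each of the time periods (24-hour, daytime and nighttime"), using the model of Section 8.2.

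SAP 2.8.3 carries over six of the seven listed parameters. The missing one is CV.

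**The concern.** A model whose records are days needs one CV per day and window. Times in a glucose band survive that step, because averaging ten daily values returns the 10-day value when days are equally complete. A CV does not: its SD is measured around the mean of whichever block of readings is used, and with a one-day block any shift of a whole day up or down disappears before modelling starts.

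The spread of daily mean glucose then goes into the residual of the mean-glucose model. No regimen-specific residual variance is planned, so it is not compared there either.

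The trial compares one bedtime dose with three pre-meal doses. Whether glucose is equally reproducible from day to day, or night to night, is a natural question under primary objective 2. A report of similar CV under both regimens could be read as answering it when the statistic could hardly have shown otherwise.

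**Working it through.** **Inputs.** The documents supply the 10 days per regimen, the three time windows, and 24 (Protocol 8.1) or about 26 subjects (SAP 2.11). Both sections say there are no estimates of means or SDs, so there is no planned figure to reproduce. All glucose values below are assumptions.

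**Step 1: variance split.** Let *m* be mean glucose, *w* the SD of readings around their own day's mean, and *b* the SD of the daily means. With ten days sampled, the between-day part enters with factor 9/10:

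- pooled 10-day CV ≈ √(w² + 0.9b²) / m
- mean daily CV ≈ (w/m)(1 + b²/m²)

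The second factor in the daily CV arises only because each day is divided by its own mean. The between-day SD itself does not enter the numerator.

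**Step 2: 24-hour window, m = 165, w = 50.** Here w/m = 30.3%.

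| b (mg/dL) | w² + 0.9b² | Pooled CV | Rise from b = 15 | Mean daily CV | Rise from b = 15 |
|---|---|---|---|---|---|
| 15 | 2702.5 | 31.5% | – | 30.6% | – |
| 20 | 2860.0 | 32.4% | 0.9 | 30.8% | 0.2 |
| 25 | 3062.5 | 33.5% | 2.0 | 31.0% | 0.5 |
| 35 | 3602.5 | 36.4% | 4.9 | 31.7% | 1.1 |

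Rises are taken before rounding. Simulations with autocorrelated readings and the same mean and SDs agree on the changes: for b from 15 to 35, pooled CV rose by 4.3 to 4.8 points and mean daily CV by 0.4 to 1.1. Their absolute CVs are lower, because autocorrelation moves part of the SD of 50 into the daily means.

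**Step 3: night window, m = 150, w = 30.** Raising the between-night SD from 25 to 45 moves the pooled CV from √1462.5/150 = 25.5% to √2722.5/150 = 34.8%. The mean nightly CV moves from 20.6% to 21.8%. This is a large contrast, shown as an upper illustration.

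**Step 4: what a test would see.** A crossover was simulated with 24 or 26 subjects, mean 160, w = 50, 96 readings a day, readings limited to 40–400 mg/dL, and 300 runs per setting. A paired two-sided 5% test was used, without the plan's insulin and carbohydrate covariates. The difference between regimens was confined to b.

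| b, one regimen vs other | Mean daily CV: difference (points) | Rejected | Pooled CV: difference (points) | Rejected |
|---|---|---|---|---|
| 15 vs 15 | 0.0 | 2% | 0.0 | 1–3% |
| 15 vs 25 | 0.2–0.3 | 2–3% | 1.9–2.0 | 39–48% |
| 15 vs 35 | 0.5 | 4–5% | 4.4–4.5 | 96–98% |
| 15 vs 45 | 0.7–0.8 | 6% | 7.4 | 100% |

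The daily-CV analysis rejects at about the false-positive rate throughout. Mean 24-hour glucose is equally insensitive (2–7%).

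**Step 5: the other planned parameters.** In the same simulation at 15 vs 35, rejection was 57–67% for time in range, 76–79% for time >250 and 70–80% for time <70. At 15 vs 25 it was 16–23%.

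**The case against.** **The daily CV is inferred.** Protocol 8.4 writes the day-by-day derivation only for AUC, and no CV formula exists. In the SAP, the sentence on all CGM parameters follows a list without CV, so the clearest documented defect there is that an endpoint has no derivation. This stands. The inference still holds for the Protocol: its list includes CV, and its only CGM model takes one record per day.

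**The endpoint wording does not define a pooled CV.** The final 10 days are the data window for insulin amounts, mean glucose and time in range too. A within-day CV averaged over those days fits the words. A reader might infer that the reported CV would simply be wrong or too low for the named endpoint; the documents do not support that. Which CV is meant is an estimand choice that the plan has left open.

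**The trial is not blind to day-to-day swings.** A reader might infer that a regimen difference in them could not be seen at all. Step 5 shows otherwise, and the SAP also plans individual glucose figures and listings. What remains is that these measures respond equally to within-day swings or a shift in mean, so they cannot attribute a difference to reproducibility.

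**The contrasts are assumed, and the larger ones are favourable to the point.** From 15 to 20 mg/dL even the pooled CV moves by only about 1 point, and at 15 vs 25 the corrected analysis would detect a difference in fewer than half of trials.

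**No mechanism is documented.** The Protocol's Introduction mentions delayed onset but says nothing about night-to-night variability after a bedtime dose. The point therefore rests on what the statistic can measure, not on an expected effect.

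**Conclusion.** The point holds for the CV endpoint. Followed as written, the Protocol analyses a within-day CV, and the SAP derives none. The CV analysis would be nearly insensitive to a QD–TID difference in day-to-day or night-to-night reproducibility: about 1 point or less, where the pooled CV would move by about 1, 2 or 4–5 points (24-hour case in the working). The direction follows from the variance split and needs no assumption; the size rests entirely on assumed SDs, a common mean and a common within-day SD.

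This is one secondary parameter in an unpowered Phase 2 study. It merits correction because CV is the plan's only dispersion measure for a primary objective and the data are already collected. It does not put the primary endpoints in doubt.

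**What to change.** - In SAP 2.8.3, restore CV to the derived parameters. There and in Protocol 8.4, define it as the SD divided by the mean of all CGM readings in the final 10 days, per subject, regimen and time window. Compute the baseline value the same way from the run-in.
- Analyse one value per subject and regimen in the crossover model (subject, period, regimen) instead of the daily-record model.
- Report mean daily CV as supportive, labelled within-day. The SD of the ten daily means could be added to show the between-day part alone.
- State a minimum number of usable days. The between-day factor is (D − 1)/D for D days, and the ±2-day visit windows let D vary.

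**Cost.** Wording in both documents and one extra derivation, with no new data. CV is left with one record per subject and regimen instead of ten, although ten daily CVs are not ten estimates of 10-day variability. Pooled CV mixes within-day and between-day variation, which is why both measures should be shown.
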